8.9 Schedule of Activities (Study Table)

	Screen	Day 0	Day 1	Wk. 1	Wk. 4	Wk. 16	Wk. 24	Wk. 36	Wk. 52
Visit Window	-60 days		+3 days	± 3 days	±3 days	± 2 weeks	± 3 weeks	± 3 weeks	± 4 weeks
Informed consent (study and surgical)	X								
Demographic data	X								
Medical/surgical history/chart review	X								
Review of Systems	X								
BCVA ***	X								
Slit-lamp exam***	X								
IOP ***	X								
Funduscopy/ Ultrasound B-scan (if necessary)***	X								
Contact Lens Review									
Pregnancy Test*	X								
Cornea thickness as measured by AS-OCT									
Slit Lamp Photography***	X								
Review Adverse Events									
Concomitant Medication Check	X								

Subjects will be instructed to strictly follow the study visit schedule.

* An additional urine pregnancy test needs to be performed just prior to surgery if there is greater than 30 days between screening visit and surgery.

**All subjects will be followed for at least 2 years. Following week 52 visit, standard of care visits will occur every 6 months for an additional 3 years or until study closure.

*** Historical results for best corrected VA, intraocular pressure, slit lamp examine, slit lamp photography and funduscopy can be used if completed within 60 days prior to screening visit

9. SAFETY AND EFFECTIVENESS ASSESSMENTS

9.1 Safety Assessments

The safety of the study intervention will be evaluated at every visit following surgery and will be defined by the incidence of related adverse events. Specifically, we will evaluate:

- **Systemic safety:** Incidence and severity of systemic adverse events during the study (based on physical examination, subject self-reporting, and changes in vital sign).
- **Ocular safety:** Incidence and severity of ocular adverse events during the study (ophthalmic examination, adverse events spontaneously reported). Ocular adverse events of special interest will include Infections Keratitis, Positive fungal rim culture and Retinal Detachment

All adverse events will be reviewed by the site investigator within 24 hours of notification and reported on the following schedule:

- Possibly, Probably, or Definitely Related **Expected AE** – Report to IRB on annual basis (continuing review)
- Possibly, Probably, or Definitely Related **Expected Serious AE** – Report to IRB on annual basis (continuing review)
- Possibly, Probably, or Definitely Related **Unexpected AE** – Report to IRB within 5 business days of discovery of event.
- Possibly, Probably, or Definitely Related **Unanticipated Problem** – Report to IRB within 5 business days discovery of event (24 hours for death or data loss)
- Possibly, Probably, or Definitely Related **Unexpected Serious AE** – Report to IRB within 5 business days of discovery of event

The Medical Monitor (DSMC Chair), [name] is required to review all unanticipated problems involving risks to subjects or others, serious adverse events, and subject deaths. The monitor must comment on the outcomes of the event, the relationship of the event to participation in the study, and must indicate whether he concurs with the details of the report provided by the principal investigator. The Medical Monitor, is responsible to oversee the safety

of the research and report observations/findings to the IRB or a designated institutional official. The Medical Monitor will review all unanticipated problems involving risks to subjects or others associated with the protocol and provide an independent report of the event to the IRB. The Medical Monitor may discuss the research protocol with the investigators; shall have authority to stop a research protocol in progress, remove individual human subjects from a research protocol, and take whatever steps are necessary to protect the safety and well-being of human subjects until the IRB can assess the monitor's report; and shall have the responsibility to promptly report their observations and findings to the IRB or other designated official and the HRPO.

- Reports for events determined by either the investigator or Medical Monitor to be possibly or definitely related to participation in the study must be promptly forwarded to the USAMRMC ORP HRPO
- Reports of events resulting in death must be promptly forwarded to the USAMRMC ORP HRPO

9.2 Surgery Related Adverse Events

A surgical related adverse event is any adverse event that is related to or possibly related to the Boston Keratoprosthesis surgical procedure. Any surgical related, normal and expected postoperative complaints or symptoms (adverse events) that occur within 30 days of surgery (week 4 visit) are not required to be reported as adverse events, unless the event involves a clinically significant change in severity or duration of symptoms or requires clinical intervention that is different from ordinary postoperative care. Examples include:

- Eye redness
- Epithelial defects
- Decreased vision
- Anterior chamber cell
- High eye pressure (up to 28)
- Eye pain

Other expected postoperative care complaints and symptoms that will are not required to be reported as an adverse event include: headache, incisional pain, nausea, vomiting, low grade fever, dizziness, irritability, nervousness, temporary sleep problems like insomnia or sleepiness, constipation, confusion and similar events, tenderness, throat soreness secondary to intubation,

or mild to moderate swelling and/or bruising around the implant site, back pain due to lying on the table during the procedure.

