8.5 Standard of Care Procedures

The following procedures will be performed as standard of care and included in study analysis:

- At screening:
 - Informed consent (must be obtained before screening starts and before surgery)
Record current ocular and systemic medications
 - Record significant medical/surgical history in the past 5 years
 - Record demographic data, including date of birth, sex, and race/ethnicity
 - Review of Systems
 - Constitutional, Ear/Nose/Throat, Respiratory, Cardiovascular, Gastrointestinal, Genital/Urinary, Integumentary, Musc/Skeletal, Endocrine, Heme/Lymph, Allergic/Immun, Neurologic, Psychiatric, All Others
 - Best corrected VA assessment at 4 meters (with refraction)
 - Intraocular pressure (measured by digital palpation)
 - Slit lamp examination

- Slit lamp photography

- Funduscopy (Ultrasound B-Scan will be performed, if necessary).

Historical results for best corrected VA, intraocular pressure, slit lamp examine, slit lamp photography and funduscopy can be used if completed within 60 days prior to screening visit

- At day 0:

- Keratoprosthesis implantation

- At day 1:

Day 1 visits will be performed by MEE clinical staff (physicians) that are not study investigators. Post-operative appointments with physicians are standard of care treatments for patients that have surgery. However study investigators that perform the surgery often do not hold clinical appointments every day of the week and therefore are unable to see the patients for the Day 1 visit. In order to ensure subject safety study patients are scheduled with available MEE physicians. The following procedures are performed as standard of care.

Study staff will collect the data from these exams from the subject's medical record.

- Best corrected VA assessment at 4 meters (with refraction)
- Intraocular pressure (measured by digital palpation)
- Slit lamp examination
- Funduscopy/ Ultrasound B-Scan (if necessary)

- At weeks 1, 4, 16, 24, 36, and 52:

- Best corrected VA assessment at 4 meters (with refraction)
 - Intraocular pressure (measured by digital palpation)
 - Slit lamp examination
 - Funduscopy/ Ultrasound B-Scan (if necessary)
 - Slit Lamp Photography
 - Cornea thickness as measured by AS-OCT

- At all times following day 0:
 - Topical steroids
 - Topical antibiotics
 - Bandage contact lens

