10. ADVERSE EVENT RECORDING AND REPORTING

10.1 Recording Requirements

Participants are informed of the anticipated risks of the trial during the consent process and continually asked to report any unusual ocular or systemic problems that occur during their participation in this trial to the site investigators or study staff. In addition, participants are seen regularly in site clinics as part of their standard post-surgical treatment. During each clinical examination participants will be queried about occurrence of adverse events. Slit lamp examination and ocular assessments will determine change in corneal thickness and or presence of corneal ulcers. Lastly, site investigators and study staff will be asked to report unanticipated problems or adverse events within 48 business days of discovery to the coordinating center (MEE) to allow for proper reporting.

All observed or volunteered adverse events (serious or non-serious) and abnormal test findings, regardless of study group or suspected causal relationship to the study drug will be recorded in the subjects' case histories (source data, case report form). For all adverse events, sufficient information will be pursued and/or obtained so as to permit 1) an adequate determination of the outcome of the event (i.e., whether the event should be classified as a serious adverse event) and; 2) an assessment of the causal relationship between the adverse event and the study drug.

Adverse events thought to be associated with the study drug will be followed until the event (or its sequel) or the abnormal test finding resolves or stabilizes at a level acceptable to the Sponsor-Investigator and the study Medical Monitor.

Study staff will alert the treating physician immediately of any participant complaints or problems that are expressed to them. The site investigator and/or site study staff will report any unexpected and serious adverse events to the coordinating center (MEE) within 48 hours of discovery regardless of the assumed relation to the study intervention. The site investigator and the study staff will follow the reporting guidelines below.

➤ **Causality and Severity Assessment**

The Sponsor-Investigator of the IND application and the Medical Monitor (DSMC chair) will promptly review documented adverse events to determine 1) if there is a reasonable possibility that the adverse event was caused by the study drug(s); and 2) if the adverse event meets the criteria for a serious adverse event.

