We plan to conduct a number of pre-specified analyses of secondary study endpoints. Analyses of secondary “time-to-event” type endpoints (time to retroprosthetic membrane treatment and time to occurrence of vitritis) will use the Kaplan-Meier approach with log-rank test and Cox proportional hazards regression, similar to the primary analysis for time to device loss. Comparison of cornea thickness metrics at week 1, 4, 16, 24, and 52 for treatment versus control group will be performed using the Mann-Whitney Wilcoxon test at each time point. Furthermore, mixed model will be used to examine the effect of time, treatment and interaction between them on cornea thickness. Comparison of twelve-month retention rate and incidence of delayed epithelial healing at Day 30 (week 4 visit) between groups will be performed using Chi-square

test, or Fisher's exact test as appropriate. In addition, the occurrence of any adverse events will be described and compared between treatment arms of the study.

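### The 30-day reporting exemption makes the adverse-event comparison less sensitive to ordinary early findings, and its pressure limit of 28 cannot be applied to pressure judged by digital palpation

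*Protocol*

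**What the plan says.** Protocol 9.2 covers events that are "related to or possibly related to the Boston Keratoprosthesis surgical procedure". Within that class it singles out "Any surgical related, normal and expected postoperative complaints or symptoms (adverse events) that occur within 30 days of surgery (week 4 visit"). Of these it says that they "are not required to be reported as adverse events, unless the event involves a clinically significant change in severity or duration of symptoms". The sentence then adds a second exception: "or requires clinical intervention that is different from ordinary postoperative care". The listed examples are redness, epithelial defects, decreased vision, anterior chamber cell, eye pain and "High eye pressure (up to 28"). No grade is given for cell, no amount for vision and no unit for pressure.

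Protocol 8.5 gives the pressure method at screening, day 1 and weeks 1 to 52: "Intraocular pressure (measured by digital palpation").

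Protocol 10.1 sets a recording rule: "All observed or volunteered adverse events (serious or non-serious) and abnormal test findings, regardless of study group" or suspected cause, go into the source data and case report form.

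Safety is Objective 1 (protocol 2.1), and 9.1 defines it through the incidence of related adverse events. The planned analysis is that "the occurrence of any adverse events will be described and compared between treatment arms of the study" (protocol 11.5, repeated in the SAP under Secondary Analysis).

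**The concern.** In a randomized safety comparison, a harm of the treated tissue can appear as a common, individually unremarkable finding that is simply more frequent in one arm. Section 9.2 removes that kind of finding from required reporting in the first month. The tissue under test is implanted in the operation to which the finding is attributed, so nearly any early ocular finding can be called possibly surgical. No rule separates a surgical effect from a tissue effect, and a masked site has no means of doing so.

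At stake is how similar adverse-event tables would be read. They could be taken as evidence of early safety when the plan does not ensure that the common early findings were counted. The pressure rule adds a second difficulty: sites have no written way to decide which pressures fall inside the exemption.

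**Working it through.** The plan has no figure to reproduce here; 28 is a reporting limit, not a calculated quantity. The check is a comparison of sections, followed by arithmetic on what under-reporting does.

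**1. What falls in the window.** Protocol 8.5 schedules visual acuity, pressure and slit-lamp examination at day 1, week 1 and week 4. That is 3 examinations per eye, or 3 × 68 = 204 if all 68 eyes in the SAP attended every visit (an assumption). The window has two end points: week 4 is day 28 ± 3 (8.6), so days 25 to 31, which does not coincide with 30 days.

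**2. What the two exceptions catch.** Both are judged patient by patient against what is usual after surgery. They catch the unusual case. They do not catch a difference in frequency between arms among usual cases.

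**3. Which events feed the comparison.** Section 9.2 governs reporting and 10.1 governs recording, so both can be followed at once. But 11.5, 11.6 and the SAP refer only to any adverse events, without saying whether a recorded but unreported finding counts. The same gap affects the A/B-coded data sent to the monitoring committee (12.1).

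**4. What else is analysed early.**

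| Early finding | By-arm analysis outside adverse events |
|---|---|
| Epithelial defect persisting to day 30 | Yes: delayed healing, chi-square or Fisher's exact |
| Epithelial defect healed earlier | None |
| Corneal thickness | Yes: AS-OCT at weeks 1 and 4 |
| Vitritis | Yes: timed from surgery |
| Anterior chamber cell | None |
| Visual acuity | None |
| Pressure | None |

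The adverse events of special interest in 9.1 (infectious keratitis, positive fungal rim culture, retinal detachment) are not on the exemption list.

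**5. What under-reporting does.** Let a share r of findings be reported, equal in both arms because sites are masked. The reported difference is r × p_T − r × p_C = r(p_T − p_C). The ratio p_T/p_C is unchanged in expectation. An excess in either arm shrinks alike; its sign does not change.

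**6. Illustration of lost sensitivity.** Assumptions: 34 eyes per arm (68/2; the SAP gives no split), two-sided 0.05, and rates chosen only to show a range. Power = Φ{[|p_T − p_C| − 1.96√(2p̄(1 − p̄)/n)] / √[(p_C(1 − p_C) + p_T(1 − p_T))/n]}, where p̄ is the mean of the two rates. For 30% vs 60%:

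- r = 1: (0.30 − 1.96√(2 × 0.45 × 0.55/34)) / √((0.21 + 0.24)/34) = (0.300 − 0.236)/0.115 = 0.55, power 0.71.
- r = 0.5 (15% vs 30%): (0.150 − 0.199)/0.100 = −0.49, power 0.31.

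| Assumed true rates | r = 1 | r = 0.5 |
|---|---|---|
| 10% vs 30% | 0.54 | 0.28 |
| 30% vs 50% | 0.39 | 0.17 |
| 30% vs 60% | 0.71 | 0.31 |

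Power is modest even with full capture, so any added tables should be descriptive.

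**7. Pressure.** Palpation yields a judgement of firmness, not a reading. The figure 28 therefore cannot be applied by the method in 8.5.

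**The case against.** The strongest reply is that 9.2 is narrow. It exempts only expected findings and keeps reportable anything that departs from the usual course or needs unusual treatment. Section 10.1 still requires everything to be recorded, and no section confines the by-arm comparison to reported events. Persistent epithelial defects, vitritis, early thickness and the events of special interest are analysed regardless. Both arms are de-epithelialized and given riboflavin (6.1), the patient is not exposed to UVA (1.2), and the rule treats both arms alike. The documents do not say that a tissue effect is expected in the first month.

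Most of this stands, and it rules out three stronger readings that a reader might infer:

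- That the trial cannot see early harm. The two exceptions and the separately analysed outcomes contradict this.
- That 10.1 says the opposite of 9.2. One is about recording and the other about reporting; what is missing is the link between them.
- That delayed healing at day 30 is the only early outcome. AS-OCT, vitritis and surgery for melt also run from the first weeks or from surgery.

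The reply does not reach the residue. No early by-arm analysis of anterior chamber cell, visual acuity or pressure is planned, and the set of events entering the comparison is undefined. On pressure there is no answer in the documents.

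**Conclusion.** The point holds in a limited form. Following 9.2 as written makes the adverse-event comparison less sensitive to early, ordinary-severity findings, chiefly anterior chamber cell, decreased vision, raised pressure and epithelial defects that heal before day 30. Whether sensitivity is actually lost depends on whether the analysis uses recorded or only reported events, which neither document settles. The loss would hide an excess in either arm and does not favour one, provided masking holds and sites apply the exemption alike in both arms.

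Its size is unknown: the documents give no early event rates, no reporting share and no arm split. The power figures above rest on assumed rates and show only that the loss could be material.

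The mismatch between the limit of 28 and digital palpation does not depend on any of these assumptions. The two sections must be reconciled. The point deserves action before the safety analysis, but it does not affect the primary efficacy endpoint.

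**What to change.** - **Analysis set.** Keep the reporting exemption, but state in protocol 9.2 and 11.6 and in the SAP that the by-arm safety comparison uses all events and findings recorded under 10.1, including those exempt from reporting.
- **SAP tables.** Tabulate by arm, at day 1, week 1 and week 4: epithelial defect, anterior chamber cell where the slit-lamp record allows, change in best-corrected acuity, and pressure as recorded. Label them descriptive safety output, with the number of eyes examined at each visit.
- **Pressure.** Reconcile 8.5 and 9.2 so that the exemption is expressed on the scale actually recorded, with its unit. No threshold is proposed here.
- **Window.** State whether the exemption ends at 30 days or at the week 4 visit.

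The cost is some wording and a few extra tables, which will show expected post-operative findings in both arms. The SAP reports 68 eyes implanted between 2017 and 2020, so new wording in 9.2 cannot change what was captured for them; the SAP tables are the main remedy. The examinations were scheduled, but the documents do not show that anterior chamber cell was recorded in a form that can be tabulated. Day 1 data are drawn from the medical record (8.5), so check this first.

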9.3 Effectiveness Assessments

The efficacy of corneal collagen cross-linking of keratoprosthesis carrier tissue in high-risk keratoprosthesis implantation will be judged using the following parameters and time points:

Primary endpoints or outcome measure(s)

- Time from surgery to device loss or replacement

Secondary endpoints or outcome measure(s)

- Twelve-month retention rate
- Incidence of delayed epithelial healing at day 30 (week 4 visit)
- Cornea thickness metrics measured by AS-OCT; at week(s) 1, 4, 16, 24, 36, and 52.
- Time from surgery to retroprosthetic membrane treatment (laser or surgical interventions)
- Time from surgery to occurrence of vitritis (sterile or infectious)
- Time from surgery to occurrence of ocular surgery to address melt, including partial graft.

10. ADVERSE EVENT RECORDING AND REPORTING

10.1 Recording Requirements

Participants are informed of the anticipated risks of the trial during the consent process and continually asked to report any unusual ocular or systemic problems that occur during their participation in this trial to the site investigators or study staff. In addition, participants are seen regularly in site clinics as part of their standard post-surgical treatment. During each clinical examination participants will be queried about occurrence of adverse events. Slit lamp examination and ocular assessments will determine change in corneal thickness and or presence of corneal ulcers. Lastly, site investigators and study staff will be asked to report unanticipated problems or adverse events within 48 business days of discovery to the coordinating center (MEE) to allow for proper reporting.

All observed or volunteered adverse events (serious or non-serious) and abnormal test findings, regardless of study group or suspected causal relationship to the study drug will be recorded in the subjects' case histories (source data, case report form). For all adverse events, sufficient information will be pursued and/or obtained so as to permit 1) an adequate determination of the outcome of the event (i.e., whether the event should be classified as a serious adverse event) and; 2) an assessment of the causal relationship between the adverse event and the study drug.

Adverse events thought to be associated with the study drug will be followed until the event (or its sequel) or the abnormal test finding resolves or stabilizes at a level acceptable to the Sponsor-Investigator and the study Medical Monitor.

Study staff will alert the treating physician immediately of any participant complaints or problems that are expressed to them. The site investigator and/or site study staff will report any unexpected and serious adverse events to the coordinating center (MEE) within 48 hours of discovery regardless of the assumed relation to the study intervention. The site investigator and the study staff will follow the reporting guidelines below.

➤ **Causality and Severity Assessment**

The Sponsor-Investigator of the IND application and the Medical Monitor (DSMC chair) will promptly review documented adverse events to determine 1) if there is a reasonable possibility that the adverse event was caused by the study drug(s); and 2) if the adverse event meets the criteria for a serious adverse event.

If the Sponsor-Investigator's and Medical Monitor's final determination of causality is "unknown and of questionable relationship to the study drug", the adverse event will be classified as associated with the use of the study drug for reporting purposes. If the Sponsor-Investigator's and Medical Monitor's final determination of causality is "unknown but not related to the study drug", this determination and the rationale for the determination will be documented in the respective subject's case history (source data or case report form).

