Subjects will be followed up post-operatively by the site investigators as standard for this procedure. This will include visits at Day 1, Weeks 1, 4, 16, 24, 36, and 52, . Subjects following Boston KPro surgery are typically seen every 6months after one year follow-up. However, some may need to be seen more regularly if they require more frequent monitoring for conditions such as glaucoma. The investigators will monitor for systemic and ocular adverse events at all follow-up visits. All adverse events will be reported to the principal investigator and Medical Monitor; and then to the MEEI HSC, sub-sites, DOD, and FDA per the specified guidelines.

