10.2 Reporting Procedures

➤ **Reporting of Adverse Events to FDA**

- **Written IND Safety Reports (if applicable)**
- **Telephoned IND Safety Reports – Fatal or life-threatening suspected adverse reactions**

➤ **Reporting Adverse Events to the Partner Human Research Committee**

The Partners Human Research Committee (PHRC) policy for "REPORTING ADVERSE EVENTS AND UNANTICIPATED PROBLEMS" will be followed.

➤ **Reporting Adverse Events to External Parties**

Adverse events will be reported to the USArmy's Human Research Protections Office (HRPO) and the US Food and Drug Administration per their guidelines. Certain adverse events, specifically infections with positive donor rim cultures, that are related to the cornea donor tissue will be reported to CorneaGen within 48 hours of discovery.

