11.6 Safety Analysis

Any adverse events, ocular or systemic, from all subjects will be utilized to summarize safety data for this study. The severity of each adverse event and the relationship of the event to the study medication will be assessed. If adverse events occur, the first concern will be the safety of the study participants. Any serious adverse event occurring during the study will be immediately reported to the principal investigator, and then to the PHRC, sub-sites, DOD, and FDA per the specified guidelines. The Research Monitor shall have the authority to stop the protocol, remove subjects from the protocol, and take any necessary steps to protect the safety and well-being of subjects until the IRB can assess the monitor's report. The monitor shall promptly report their observations and finding to the IRB or other designated official.

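### Protocol 10.1 gives sites 48 business days to report adverse events to the coordinating center, which does not fit the IRB limits in 9.1 or the immediate rule for serious events in 11.6

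*Protocol*

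**What the plan says.** The time limits are spread over five sections of the protocol.

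- **10.1 Recording Requirements, general rule.** Sites are asked to "report unanticipated problems or adverse events within 48 business days of discovery to the coordinating center (MEE) to allow for proper reporting".
- **10.1, narrower rule.** Sites must "report any unexpected and serious adverse events to the coordinating center (MEE) within 48 hours of discovery", whatever the presumed relation to the intervention.
- **10.1, causality and severity.** The Sponsor-Investigator and "the Medical Monitor (DSMC chair) will promptly review documented adverse events to determine" whether each event may have been caused by the study drug and whether it is serious.
- **3.1 Study Design Description.** "All adverse events will be reported to the principal investigator and Medical Monitor; and then to the MEEI HSC, sub-sites, DOD, and FDA", under the applicable guidelines.
- **9.1 Safety Assessments.** The site investigator reviews each event within 24 hours of notification, and a schedule follows. For related unexpected adverse events, serious or not, it reads "Report to IRB within 5 business days of discovery of event". For related unanticipated problems it reads "Report to IRB within 5 business days discovery of event (24 hours for death or data loss", in brackets. Related expected events, serious or not, go to the IRB once a year.
- **10.2 Reporting Procedures.** Infections with positive donor rim cultures "that are related to the cornea donor tissue will be reported to CorneaGen within 48 hours of discovery".
- **11.6 Safety Analysis.** "Any serious adverse event occurring during the study will be immediately reported to the principal investigator", and after that to the ethics committee, sub-sites, DOD and FDA.

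**The concern.** The general rule in 10.1 exists so that onward reporting can be done properly, yet its window is far longer than the onward deadlines. Sections 3.1 and 11.6 place the principal investigator ahead of the ethics committee and the agencies. The short IRB limits in 9.1 apply only to related events, and 10.1 gives the final decision on relatedness and seriousness to the Sponsor-Investigator and Medical Monitor. Section 9.1 also requires the Medical Monitor to review every unanticipated problem and to report on it independently to the IRB. None of these people can act promptly on an event that a site may properly hold for more than nine weeks.

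Safety is Objective 1 of this phase I/II trial, and randomization was planned over 16 centers. The risk is that a site follows 10.1 to the letter while those responsible for safety oversight learn of an event after its IRB deadline. The problem is one of safety reporting and has no bearing on the efficacy inference.

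**Working it through.** **Length of the window.** The input is 48 business days (10.1). I assume a five-day working week and ignore holidays.

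- 48 / 5 = 9.6 working weeks, that is, 9 weeks and 3 business days.
- Discovery on Monday or Tuesday: 63 + 3 = 66 calendar days.
- Discovery on Wednesday, Thursday or Friday: the last 3 business days cross a weekend, so 63 + 5 = 68.
- Discovery on Saturday: 67. On Sunday: 66.

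**Against the 5-business-day IRB limit (9.1).** Five business days span 7 calendar days from a weekday, 6 from Saturday and 5 from Sunday.

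- Excess in business days: 48 − 5 = 43.
- Excess in calendar days: 66 − 7 = 59 (Monday, Tuesday); 68 − 7 = 61 (Wednesday to Friday); 67 − 6 = 61 (Saturday); 66 − 5 = 61 (Sunday).
- Ratio: 48 / 5 = 9.6.

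**Against the 48-hour limits (10.1 and 10.2).** 66 / 2 = 33 to 68 / 2 = 34 times as long. This ratio only shows scale, because the 48-hour limits cover unexpected serious events and donor-tissue infections, not the class with the clearest gap.

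**By event class**

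| Event class | Site to center (10.1) | Other limit | Fit |
|---|---|---|---|
| Related non-serious unexpected event, or related unanticipated problem that is not a serious adverse event | 48 business days | IRB: 5 business days (9.1) | Conflict; no shorter rule applies |
| Related unanticipated problem involving death or data loss | 48 business days, or 48 hours if also an unexpected serious event | IRB: 24 hours (9.1) | Both exceed 24 hours |
| Expected serious event | 48 business days | Principal investigator: immediately (11.6); IRB: yearly if related (9.1) | Conflict with 11.6 only |
| Unexpected serious event | 48 hours | IRB: 5 business days if related (9.1); principal investigator: immediately (11.6) | Fits the IRB limit; 48 hours is not immediate |
| Non-serious donor-tissue infection | 48 business days | Eye bank: 48 hours (10.2) | Conflict only if the report goes through the center |
| Expected non-serious event | 48 business days | IRB: yearly if related (9.1) | No conflict |

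**Who files, and from when.** The IRB schedule in 9.1 and the eye-bank rule in 10.2 are in the passive voice. Neither states who files or whether discovery means discovery by the site or by the center.

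**The case against.** The strongest counter-argument is that sites may file with their IRBs themselves. Section 9.1 opens its schedule with review by the site investigator within 24 hours, and 8.2.2, 12.1 and 14.1 all refer to the sites' own IRBs. On that reading the 48 business days is only an outer limit for informing the center, and a site that obeys the stricter rule each time breaks none. The data capture system (13.1) may also show events to the center earlier. The figure could well be a slip, since 48 hours appears elsewhere in 10.1 and in 10.2. Finally, the SAP reports 68 implants in 2017–2020, so a correction now helps only the follow-up that remains.

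Much of this stands. Harm depends on the routing, a late report is not inevitable, and several event classes are little affected or not at all. It does not remove the conflict. The 24-hour review brings the event to the site investigator, not to the center, and leaves the filer unnamed. The data system has no stated entry deadline. Direct filing by a site does not put the event before the people who make the final decision on relatedness and seriousness. If the number is a slip, the documents do not show what was meant, and sites have to work from the written text. One shorter limit could also cure the problem without tiers, provided it met every onward deadline.

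**Conclusion.** The concern holds and should be fixed. For related non-serious unexpected events, and for related unanticipated problems that are not serious adverse events, the site-to-center window exceeds the IRB limit by 43 business days (59 to 61 calendar days), with no shorter rule in reserve. For expected serious events the same window contradicts 11.6. For unexpected serious events the remaining mismatch is smaller: 48 hours against immediately, and against 24 hours where an unanticipated problem involves death or data loss.

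The figures assume a five-day week, no holidays and both clocks starting at site discovery. I read the 48-hour sentence in 10.1 as covering events that are both unexpected and serious. If it were meant to cover events that are either, 10.1 would contradict itself on those events, and unanticipated problems that are neither would still be exposed. A deadline is actually missed only if the report goes through the center or waits for the center's decision on relatedness. Sample size, power, endpoints and analysis are untouched.

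**What to change.** Correct the 48-business-day sentence in 10.1 and reconcile it with 9.1, 10.2 and 11.6. Set site-to-center limits by event class so that each falls within the protocol's own onward deadline:

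- unanticipated problems involving death or data loss (24 hours to the IRB);
- serious adverse events, where the 48 hours in 10.1 and the immediate rule in 11.6 must be made to agree;
- donor-tissue infections (48 hours to the eye bank);
- related non-serious unexpected events and other unanticipated problems (5 business days to the IRB).

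Expected non-serious events can keep a longer limit. A single limit short enough for every deadline would also do. For each class, state who files and whose discovery starts the clock.

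The cost is low: a clarification or minor amendment to 10.1, matching edits to the other three sections, and a notice to sites. It needs no new data and no change to the sample size or analysis.
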